3.1.2 Optional Open-label Extension

Subjects who either complete the Randomization Period of the study (up through the Test of Cure Visit), or who are prematurely discontinued from study treatment during the Randomization Period due to worsening of signs and/or symptoms of otomycosis in the judgment of the investigator, will be offered the opportunity to participate in an optional open-label extension, if they have a visual presence of fungal elements in at least one ear treated during the Randomization Period. Only the ear(s) that were treated in the Randomization Period will be potentially eligible for treatment during the Optional Open-label Extension.

All subjects in the Optional Open-label Extension will receive miconazole oil for 14 days. No unblinding of the subject's treatment in the Randomization Period will occur at this time.

Before a subject enters the Optional Open-label Extension, all procedures for the Test of Cure Visit will be completed for that subject; however, a fungal culture will not be required at this visit for subjects known to have a negative fungal culture at Screening/Baseline, as assessed after at least 14 days of incubation by the clinical laboratory performing the fungal culture.

At the first visit of the Optional Open-label Extension (Day OLE1, which will occur while the subject is already onsite for the Test of Cure or Early Termination Visit from the Randomization Period), study drug (miconazole oil) will be weighed and dispensed to the subject along with a subject diary. Subjects or their caregivers will administer the first dose of miconazole oil at the site. AEs and concomitant medications will then be assessed. Subjects will then continue to administer miconazole oil and to complete the subject diary twice per day for a total of 14 days, following the same instructions as provided at the Screening/Baseline Visit on Day 1.

Subjects will return to the clinic on Day OLE15 for the End of Treatment Visit, at which time a clinical evaluation of the signs and symptoms of otomycosis will be performed, as well as an assessment of AEs and concomitant medications. A urine pregnancy test will be performed in women of childbearing potential. The subject will return all unused miconazole oil along with the completed subject diary.

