4.3 Subject Discontinuation

A subject MAY be withdrawn from the study (at the discretion of the investigator, sponsor, and/or IRB) prior to study completion for any of the following reasons, including, but not limited to:

- A serious adverse event (SAE) occurring during the course of the study which precludes continued follow-up
- Intercurrent illness which may, in the investigator's opinion, significantly affect study assessments
- Failure to follow required study procedures
- For subjects participating in Enrollment A, a negative fungal culture at Screening/Baseline (as assessed after at least 14 days of incubation by the clinical laboratory performing the fungal cultures)

A subject MUST be discontinued prior to the final study visit for any of the following reasons:

- Whenever the subject decides it is in his/her best interest to withdraw
- Whenever the investigator decides it is in the subject's best interest to be withdrawn

Prior to discontinuing a subject, every effort should be made to contact the subject, schedule a final study visit, and obtain as much follow-up data as possible. If possible, the assessment schedule for the Test of Cure Visit (Randomization Period) or the End of Treatment Visit (Optional Open-label Extension or Enrollment B) should be performed, and an effort should be made to collect all study drug. A fungal culture is not required for subjects who are prematurely discontinued from the study.

For Enrollment A, due to the time required to obtain fungal culture results from Screening/Baseline, subjects will be enrolled into the study based on a clinical diagnosis of otomycosis (including the visible presence of fungal elements at Screening/Baseline), without a requirement for a positive fungal culture. Subjects who end up with a negative Screening/Baseline fungal culture are not required to be discontinued from the study, but these subjects will not be included in the primary efficacy analysis. Because the sponsor's goal is to have at least 128 subjects in the MITT population (see Section 10.4.2), the total number of subjects enrolled into Enrollment A may be higher or lower than 220, depending on the percentage of subjects who are eligible to be included in the MITT population.

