5.1.2 Prohibited Medications

Other than the study drug, no other topical medications (including but not limited to antibiotics, alcohol, boric acid, peroxide, and/or corticosteroids) are allowed to be used in the ear(s) being treated with study drug. Other prohibited treatments include systemic antifungal therapy, warfarin, immunosuppressive or immune-stimulating drugs, and systemic steroids. A subject who discontinues study drug during the Randomization Period and who subsequently uses a topical corticosteroid (e.g., to treat an AE such as itching) in the ear(s) that were treated with study drug during the Randomization Period will be eligible for the Optional Open-label Extension if the topical corticosteroid is discontinued in the ear(s) that will be treated with study drug before the start of study drug in the Optional Open-label Extension, and as long as the subject meets all other eligibility criteria for the Optional Open-label Extension.

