6 STUDY SCHEDULE

6.1 Enrollment A

6.1.1 Study Flow Chart

The study schedule for Enrollment A is presented in Table 3.

Table 3 Study Schedule: Enrollment A

Evaluations and Procedures:	Randomization Period				Optional OLE	
	Screen/ Baseline ^a Day 1	On Treat ^b Day 8	End of Treat ^b Day 15	Test of Cure ^c Day 22 ^d	Start of Treat Day OLE1 ^e	End of Treat Day OLE15 ^b
Informed consent/assent	X					
Inclusion/exclusion criteria	X					
Medical/medication history	X					
Physical examination	X					
Otomycosis signs and symptoms	X	X	X	X		X
Urine pregnancy test ^f	X			X		X
Randomization	X					
Dispensation of study drug	X				X	
Dispensation of subject diary	X				X	
Collection of subject diary		X ^g	X			X
Administration of study drug at site	X				X	
Weighing of study drug	X	X	X		X	X
Collection of study drug			X			X
Fungal culture ^h	X		X	X		
Ear cleaning	X	X				
AE evaluations	X	X	X	X	X	X
Concomitant medications review	X	X	X	X	X	X

- a. Procedures for this visit may occur over a 2-day period, if necessary (with Day 1 defined as the first day on which study drug is administered). All procedures for this visit must occur before the first administration of study drug with the exceptions that AE evaluations and review of concomitant medications will also occur after the start of study drug on Day 1.
- b. This visit may occur up to 3 days later than the specified day.
- c. This visit may occur up to 1 day sooner or up to 8 days later than the specified day.
- d. In case of early termination, the assessments planned for the Test of Cure Visit should be performed with the exception of fungal culture, which is not required.
- e. This visit will occur on the same day as the final visit of the Randomization Period.
- f. Females of childbearing potential only.
- g. The subject diary will be returned to the subject after review by study staff for documentation of missed and/or extra study drug doses.
- h. Samples will be used for growth and identification of fungal organisms as well as susceptibility testing to miconazole. Fungal cultures are not required to be taken at Day 15 or at Day 22 for subjects known to have a negative fungal culture at Screening/Baseline (assessed after at least 14 days of incubation by the clinical laboratory performing the fungal cultures).

OLE=Open-label Extension; Screen=Screening; Treat=Treatment

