6.1.2.4 Test of Cure (Day 22)

This visit may occur up to 1 day sooner or up to 8 days later than the specified day.

The following procedures and evaluations will occur during this visit:

- Otomycosis signs and symptoms
- Fungal culture (not required for subjects known to have a negative fungal culture at Screening/Baseline, as assessed after at least 14 days of incubation by the clinical laboratory performing the fungal culture)
- AE evaluation
- Review of concomitant medications
- Urine pregnancy test (in female subjects of childbearing potential only)

In case of early termination from the Randomization Period, the procedures planned for the Test of Cure Visit with the exception of fungal culture should be performed.

Subjects who complete the Test of Cure Visit and who have a visual presence of fungal elements in at least one ear treated during the Randomization Period will be offered the opportunity to participate in the Optional Open-label Extension.

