10.3 Sample Size

For the Randomization Period, approximately 128 subjects (~64 in each group) are required to provide 80% power, using a chi-square test with a 2-sided significance level of 0.05, assuming a response rate for the primary efficacy endpoint of 25.0% in the miconazole oil group and 7.1% in the vehicle oil group.

The sample size of 220 subjects for Enrollment A assumes that ~58% of subjects enrolled into Enrollment A will have a positive fungal culture at Screening/Baseline and will therefore be included in the MITT population. This number may be higher or lower depending on the percentage of subjects eligible to be included in the MITT population.

The estimated sample size of 170 subjects for Enrollment B is not based on statistical considerations and is instead based on the achievement of at least 300 subjects who have been exposed to miconazole oil for 14 days who are evaluable for safety (see also Section 3.4.2).

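### Culture at an early switch to open-label drug is required by 3.1.2 but waived by 6.1.2.4 and Table 3, and follow-up after stopping drug is unspecified, so mycological cure may be imputed where it could be observed

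*Combined protocol and SAP*

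**What the plan says.** **Culture before the extension.** Section 3.1.2, repeated in the synopsis, admits subjects who finish the Randomization Period and subjects taken off study treatment early for worsening. For both it states: "Before a subject enters the Optional Open-label Extension, all procedures for the Test of Cure Visit will be completed for that subject". The only culture exemption there is for a baseline culture known to be negative after at least 14 days of incubation.

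**Culture at early termination.** Table 3 note d reads: "In case of early termination, the assessments planned for the Test of Cure Visit should be performed with the exception of fungal culture". Section 6.1.2.4 says of early termination from the Randomization Period that "the procedures planned for the Test of Cure Visit with the exception of fungal culture should be performed". Neither limits the exemption to baseline-negative subjects. Section 4.3 gives a similar exemption for subjects who leave the study: "A fungal culture is not required for subjects who are prematurely discontinued from the study".

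**Timing.** Under Table 3 note e and section 6.1.3.1, the first open-label dose is given on the day of the final Randomization Period visit.

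**Stopping drug versus leaving the study.** Section 3.1.2 refers to discontinuation from treatment. Section 5.1.2 foresees "A subject who discontinues study drug during the Randomization Period and who subsequently uses a topical corticosteroid" and may still enter the extension. Section 8.5 lets a subject taken off drug for pregnancy remain in the study case by case. No section states which visits a subject attends after stopping drug.

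**Analysis.** Section 10.5.4 scores missing data as failure for the primary and secondary endpoints. Mycological cure, defined only by a negative culture, is tested first after the primary (10.5.1.1). The sensitivity analyses in 10.5.5 address the primary endpoint alone.

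**The concern.** Sites hold opposite instructions for the same visit. A baseline-positive subject, who belongs to the MITT population, must be cultured under 3.1.2 and need not be under 6.1.2.4 and Table 3. Once the open-label dose is given, no untreated-by-extension sample can be obtained. Subjects who stop drug without switching may also have no Day 22 culture, because nothing tells the site to keep them on schedule.

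Each missing culture becomes a failure on mycological cure. If more subjects stop on vehicle, as the Phase 2 adverse-event data suggest, the imputed failures may fall unevenly and favour miconazole on the first gated secondary. No planned analysis would show this. The per-protocol set would not either, since 10.4.3 retains subjects who discontinue for a related adverse event, lack of effect or worsening.

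**Working it through.** **1. Do the passages conflict?** Take a subject stopped for worsening at the Day 8 visit who has visible fungal elements and opts for the extension.
- Section 3.1.2: culture is required. The exemption cannot apply, because a negative baseline needs at least 14 days of incubation and so is not yet known.
- Section 6.1.2.4 and Table 3 note d: culture is excepted.
- Section 4.3: this concerns leaving the study, whereas the switcher leaves only randomized treatment. It should be aligned, but the direct conflict is with the other two places.

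**2. The plan's sample size.** Section 10.3 says "approximately 128 subjects (~64 in each group) are required to provide 80% power", "using a chi-square test with a 2-sided significance level of 0.05", with cure rates of "25.0% in the miconazole oil group and 7.1% in the vehicle oil group". Pooled formula, with mean rate (0.25 + 0.071)/2 = 0.1605:

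n = [1.960·√(2·0.1605·0.8395) + 0.842·√(0.25·0.75 + 0.071·0.929)]² / 0.179² = (1.017 + 0.424)² / 0.0320 = 64.8, so 65 per arm or 130 in total.

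The unpooled version gives 63 per arm. Exact power at 64 per arm is 81.0%. The plan's 128 reproduces and is not challenged. It supplies the 64 per arm used in step 5.

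**3. What Phase 2 says about stopping.** Section 1.1 states that adverse-event discontinuations were in a higher percentage of vehicle subjects. Table 2 lists terms, not subjects: nine on vehicle (N = 20, largest single term 3) and four on 14-day miconazole (N = 22, each 1). One subject may carry several terms, so the counts lie between 3 and 9 of 20 and between 1 and 4 of 22. Both 3/20 v 1/22 (15.0% v 4.5%) and 3/20 v 3/22 (15.0% v 13.6%) fit the table and the statement. Larger gaps also fit.

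**4. Artificial difference in mycological cure.** Let dV and dA be the proportions stopping without a culture on vehicle and miconazole. Let cV and cA be the shares of those subjects who would have been culture-negative. Scoring them all as failures adds dV·cV − dA·cA to the miconazole-minus-vehicle difference. The documents give no value for cV or cA; 30%, 50% and 70% are assumptions.

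| Stopping (vehicle, miconazole) | c = 30% | c = 50% | c = 70% |
|---|---|---|---|
| 3/20, 3/22 (gap 1.36 points) | 0.4 | 0.7 | 1.0 |
| 3/20, 1/22 (gap 10.45 points) | 3.1 | 5.2 | 7.3 |

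The table takes cV = cA. If cV = 30% and cA = 50%:
- 3/20 v 3/22: 15.0% × 30% − 13.6% × 50% = 4.5 − 6.8 = −2.3 points.
- 3/20 v 1/22: 4.5 − 2.3 = +2.2 points.

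The sign therefore depends on figures the documents do not contain.

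**5. Effect on the test, as an illustration.** This is exact enumeration of the chi-square test at 64 per arm. True cure is equal in both arms at p = 30%, 50% or 70%, those who stop cure as often as completers, and all who stop are scored as failures.
- All cultures observed, or 10% stopping in each arm: rejection between 4.5% and 5.4%.
- 3/20 v 3/22: 5.1%, 5.2%, 5.5%.
- 3/20 v 1/22: 7.0%, 8.9%, 14.4%, nearly all of the excess favouring miconazole.

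These rates are not conditional on passing the primary gate.

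**6. Primary endpoint.** Extension entry requires visible fungal elements in at least one treated ear. If that is the study ear, clinical cure has failed and so has therapeutic cure, whatever the culture shows. The primary could change only for an early terminator whose study ear is clear, including a bilateral case with fungal elements only in the other ear.

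**The case against.** The waiver was deliberate. The Amendment 2 rationale is that this culture would not contribute to the efficacy evaluation, and failure imputation followed an FDA comment. The endpoint is culture at Test of Cure; a Day 8 swab on drug is a different measurement, and the plan does not say it would count. This stands in part: it is why an early sample belongs in a supportive analysis only. The rationale does not hold for baseline-positive subjects, however, since they are in the MITT population and their missing culture is scored.

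Section 4.3 also asks for as much follow-up data as possible, and 4.4 lets subjects who miss a visit attend later ones. A reader might infer that 4.3 withdraws anyone who stops drug for an adverse event. It does not say so: its reasons concern leaving the study, and 8.4 records permanent discontinuation of drug as an action taken. The gap is a silence, not a rule.

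A reader might take 42% (the complement of the ~58% baseline-positive rate in 10.3) as the culture-negative share among those who stop. Those baseline-negative subjects are excluded from MITT, so the figure does not carry over. Nor does the planned tipping-point analysis have to vary these outcomes, because it covers the primary endpoint, which is largely determined without the culture.

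**Conclusion.** The contradiction between 3.1.2 and 6.1.2.4 with Table 3 note d is in the current text and needs reconciling. The protocol separates stopping drug from leaving the study but never says that subjects who stop drug stay on the Day 15 and Day 22 visits. The consequence falls on mycological cure, where missing cultures become failures without any sensitivity analysis. The primary endpoint is little affected.

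A reader might infer an established bias toward miconazole. The documents support only that it is plausible. Under equal culture-negative shares it is that share times the difference in stopping rates, which could be under 1 point or several points, and it may reverse if the shares differ by arm. That range rests on assumed shares and on small Phase 2 counts that are not reported by subject. Table 2 also mixes stopping drug with leaving the study and is not restricted to MITT subjects.

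**What to change.** 1. Reconcile 6.1.2.4 and Table 3 note d with 3.1.2, and align 4.3, so that culture is waived only for a known-negative baseline. Specify that the sample is taken before the first open-label dose.
2. State in 4.3 that stopping study drug is not withdrawal from the study. Subjects who stop drug, do not withdraw consent and do not enter the extension attend the scheduled Day 15 and Day 22 visits with scores and culture, and the Day 22 result is used in the mycological cure analysis.
3. State that early switchers count as failures in the main analyses. Label their sample Early Termination and use it in a supportive missing-data analysis of mycological cure.

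Item 2 replaces imputed values in the gated test. Item 3 leaves switchers' main-analysis result as failure but makes the dependence on that choice visible.

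The cost is amendment wording and a few more swabs and visits. Section 3.4.2 assumes ~10% of the miconazole arm stops early; if that holds in MITT, it is 64 × 10% = 6.4, about six subjects. No vehicle rate is given. Observed mycological cure on vehicle may rise slightly. The sample size stays at 128.

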4.4 Subjects Lost to Follow-up

An effort must be made to contact subjects who do not return for scheduled visits, to schedule the visit and/or obtain as much follow-up data as possible. At least three telephone calls and one certified letter must be placed to the subject after the first missed visit, to attempt to get the subject to complete the visit and to gather as much follow-up data as possible, before a subject may be considered lost to follow-up and discontinued from the study. Subjects who miss a visit may still be scheduled for a subsequent visit.

All follow-up attempts will be documented and kept with the subject's source documentation, and the applicable eCRFs will be completed. The date a subject will be considered lost to follow-up will be the date of the last non-missing visit.

5 CONCOMITANT THERAPIES

All concomitant therapies must be recorded on the eCRF.

Every effort should be made to keep concomitant therapy and dosing constant during the study. Any changes in concomitant therapies during the study must be recorded on the eCRF at each visit. The reason for any change in concomitant therapies should be reported as, or in conjunction with, an AE except as noted below:

- Prophylactic therapies, such as vaccines or prophylactic analgesics, must be recorded on the eCRF but should not be reported as AEs.
- Changes in therapy for pre-existing conditions that are not related to a worsening of the condition must be reported on the eCRF but should not be reported as AEs. The condition must be reported on the eCRF as part of the subject's medical history.

5.1 Enrollment A

In addition to all concomitant therapies, all therapies within 3 months prior to Day 1 must also be recorded on the eCRF.

5.1.1 Permitted Medications

Therapies (medication and non-medication therapies) not restricted by the protocol may be used during the study for the treatment or prevention of disease or to maintain good health. Vitamins and mineral supplements are permitted at dosages considered by the investigator as reasonable for maintaining good health. Non-prohibited chronic therapies being used at Screening/Baseline may be continued.

Oral analgesic medications such as non-steroidal anti-inflammatory drugs (NSAIDs) or acetaminophen are permitted. Such medications may be helpful for the management of pain caused by otomycosis and/or study procedures such as ear cleaning and administration of study drug.

5.1.2 Prohibited Medications

Other than the study drug, no other topical medications (including but not limited to antibiotics, alcohol, boric acid, peroxide, and/or corticosteroids) are allowed to be used in the ear(s) being treated with study drug. Other prohibited treatments include systemic antifungal therapy, warfarin, immunosuppressive or immune-stimulating drugs, and systemic steroids. A subject who discontinues study drug during the Randomization Period and who subsequently uses a topical corticosteroid (e.g., to treat an AE such as itching) in the ear(s) that were treated with study drug during the Randomization Period will be eligible for the Optional Open-label Extension if the topical corticosteroid is discontinued in the ear(s) that will be treated with study drug before the start of study drug in the Optional Open-label Extension, and as long as the subject meets all other eligibility criteria for the Optional Open-label Extension.

5.2 Enrollment B

In addition to all concomitant therapies, all therapies within 28 days prior to Day B1 must also be recorded on the eCRF.

5.2.1 Permitted Medications

Therapies (medication and non-medication therapies) not restricted by the protocol may be used during the study for the treatment or prevention of disease or to maintain good health. Vitamins and mineral supplements are permitted at dosages considered by the investigator as reasonable for maintaining good health. Non-prohibited chronic therapies being used at Screening/Baseline may be continued.

Oral analgesic medications such as NSAIDs or acetaminophen are permitted.

